CLINICAL PROTOCOL COVER PAGE

Protocol Title: A randomized, double-blind, placebo controlled, parallel clinical trial to

investigate the safety and efficacy of Bacillus coagulans SNZ 1969 on

immune health in healthy school-aged children

Protocol Number: 25SACCP01

Protocol Date: August 28, 2025

Version: 2

Study Design: Randomized, double-blind, placebo controlled, parallel clinical trial

Sponsor: SANZYME BIOLOGICS PVT LTD

[name]

India

Sponsor Contact: [name] PhD

Vice President, Scientific Affairs SANZYME BIOLOGICS PVT LTD

[name]

India

[name]

CRO: KGK Science Inc.

[name]

[name]

[name]

Canada

Medical Director

(Qualified Investigator): [name]

KGK Science Inc. [contact]

PROTOCOL SIGNATURE SHEET

The sponsor and the investigator agree to conduct the study in compliance with the clinical study protocol (and amendments), International Conference on Harmonization (ICH) guidelines for current Good Clinical Practice (GCP) and applicable regulatory requirements.

Name	Signature	Date
Sponsor: [name] PhD Vice President of Scientific Affairs SANZYME BIOLOGICS PVT LTD [name] India		24/09/2025
Contract Research Organization: [name] Director of Clinical Services KGK Science Inc. [name] Canada	[name]	Oct. 3, 2025

1 SCHEDULE OF ASSESSMENTS 1

PROCEDURES/ASSESSMENTS	V1 Screening	V2 Baseline Day 0	V3 Day 28 ± 2 (Remote)	V4 Day 56 ± 2 (Remote)	V5 Day 84 ± 2 (EOS)
Informed consent & Assent (if applicable)	•				
Review inclusion/exclusion criteria	•	•			
Review medical history	•				
Review concomitant therapies	•	•	•	•	•
Vitals: Height, weight, heart rate, blood pressure	•	•			•
Urine Pregnancy Test	•	•			•
Randomization		•			
Quantibody® Human Immune Response Array		•			•
Immunoglobulin A (IgA), G (IgG), E (IgE), and M (IgM)		•			•
Saliva sIgA		•			•
Primary Endpoint Assessment (URTI & GITI symptoms via study diary)		•	•	•	•
IP Dispensed		•			
IP Returned					•
Stool Collection Kit Dispensed	•	•			
Stool Collection Kit Returned (for Fecal Microbiome Analysis)		•			•
Study Diary Dispensed (including CARIFS, Additional Respiratory Tract Symptoms, and GITI symptom questionnaires)	• 1	•	•	•	
Study Diary Reviewed (including CARIFS, Additional Respiratory Tract Symptoms, and GITI symptom questionnaires)		•	•	•	•
Compliance Reviewed			•	•	
Compliance Calculated					•
Adverse Events		•	•	•	•

August 28, 2025 -Confidential- Page 4 of 39

¹ Participants will complete the study diary inclusive of the CARIFS questionnaire, Additional Respiratory Tract Symptoms, and GITI symptoms, during the run-in period between screening and baseline

2 LIST OF ABBREVIATIONS

AE Adverse Event

AUC Area Under the Curve

BP Blood Pressure

CARIFS Canadian Acute Respiratory Illness Flu Scales

CRO Contract Research Organization eCRF Electronic Case Report Form

etc. "and so forth" e.g. "for example"

GCP Good Clinical Practice

GITI Gastrointestinal Tract Infection

HR Heart Rate

ICF Informed Consent Form

ICH International Conference of Harmonization

Ig Immunoglobulin *i.e.* "in other words"

IEC Independent Ethics Committee

IP Investigational Product
IRB Institutional Review Board

ITT Intention to Treat

kg Kilogram mL Milliliter

NNHPD Natural and Non-Prescription Health Product Directorate

OTC Over the Counter PP Per Protocol

QI Qualified Investigator SAE Serious Adverse Event

URTI Upper Respiratory Tract Infection

4 INTRODUCTION

The flu season in North America typically occurs between late November and March (1,2). A typical year in Canada sees 12,200 hospitalizations and approximately 3,500 deaths due to flu (3). In the United States, over 200,000 hospitalizations and over 30,000 deaths (4) occur due to respiratory infections, which creates a large economic burden of \$40 billion/year and \$87 billion/year for the common cold (5) and influenza, respectively (6). Worldwide seasonal influenza can cause one billion infections, leading to three-to-five million severe cases, and from 250,000 to 500,000 deaths world-wide each year (1). The influenza vaccine is effective in providing protection against infection and illness from influenza (2), however a small percentage of school age children receive the flu vaccine. Overall, 31% of children 6 months to 17 years received the seasonal influenza vaccine during the 2023-2024 influenza season (7). Furthermore, rotavirus (RV) is a common cause of gastroenteritis in children; approximately 36% of children with RV gastroenteritis see a physician, 15% visit an emergency department, and 7% require hospitalization (8). Most unimmunized children are infected by 5 years of age whereas the first infection usually does not lead to immunity. In Canada RV is a common cause of gastroenteritis accounting for 10% to 40% of all childhood gastroenteritis (8). Similarly, norovirus is an increasingly important player in childhood gastroenteritis with the uptake in rotavirus vaccination (9). A meta-analysis on 6 years of research from 2014-2020 found the pooled prevalence of norovirus infection among 120,531 children with gastroenteritis from 45 countries was 17.7% (9).

The common cold is highly prevalent in the under 12 population (10), with the most common methods to reduce the risk of catching the cold being to wash your hands and avoid contact with your face. For adults with a severe cold, medications exist with codeine or hydrocodone, however, these are not recommended for children under 18 years of age (11). Further, decongestants are not advised in children 6-12 years of age (10). Almost one-third of common cold cases in children result in a visit to a physician, and over 75% of parents report giving their children over-the-counter (OTC) cold medication. However, there is little evidence these therapies are effective for children (12). Consequently, there is an increased need to determine efficacious alternatives that are safe. There have been several dietary supplements known to have immunomodulating effects examined in children, yet results are inconsistent. A meta-analysis of 31 randomized, placebo-controlled trials investigating the effects of regular vitamin C supplementation found a reduction in cold duration in adults and children (13). However, the effect of other supplements, such as echinacea, zinc, and garlic, are not as efficacious or clear. A meta-analysis examining the effects of echinacea involving 12 placebo-controlled randomized clinical trials (one involving children) showed no benefit for the common cold (14). In a meta-analysis investigating the effects of zinc supplementation on common cold symptoms results showed no benefit for children across three randomized, placebo-controlled trials (15). Another meta-analysis for preventing the common cold with garlic showed a reduction in incidence of common cold, however, more randomized, placebo-controlled trials are needed as only a single trial met these criteria (16). There is a noticeable lack of options for natural health supplements that provide strong evidence for reducing the burden of cold and flu-like symptoms for children, even though they are at the highest risk for catching common colds.

The current study will examine the efficacy of *Bacillus coagulans SNZ 1969 (B. coagulans)* on immune health in children attending school. The primary outcome will assess the difference between the investigational product and placebo from baseline to day 84 in incidence, duration, and severity of (1) Upper Respiratory Tract Infection (URTI) and (2) Gastrointestinal Tract Infection (GITI) symptoms. This will be assessed by use of the Canadian Acute Respiratory Illness and Flu Scale (CARIFS) and a GITI symptoms questionnaire. A randomized, double-blind placebo controlled study of healthy school aged children (6-8

years) evaluating *B. coagulans* demonstrated a significant decrease in incidence of Upper Respiratory Tract Infections (URTIs) symptoms including nasal congestion, bloody nasal mucus, itchy nose, and hoarseness (17). There were corresponding decreases in duration of URTI symptoms of hoarseness, headache, red eyes and fatigue (17). In the same study *B. coagulans* significantly decreased the incidence of flatulence, a potentially symptom of GITI. These beneficial effects were associated with modulation of serum immune markers for TNFα, CD163, G-CSF, ICAM-1, IL-6, IL-8, MCP-2, RAGE, uPAR, and PF4 (17). Similarly, a randomized double blind placebo control study of malnourished children between 1 and 5 years of age demonstrated a significant reduction in the total days of illness with *B. coagulans SNZ 1969*® compared to placebo over a period of 3 months (18). This study also demonstrated a non-significant reduction gastrointestinal and respiratory tract infections along with a shorter duration of infection (18).

Enrolled participants will include children 6-12 years of age currently attending school during the 2025-2026 cold and flu season to allow for adequate exposure to URTI or GITI pathogens. To avoid confounding effects of pre-existing medical conditions children presenting with a history or presence of a clinically relevant respiratory, pulmonary, or gastrointestinal condition will be excluded at the discretion of the Qualified Investigator. Furthermore, participants consuming immune modulating medications, antibiotics, products containing *B. coagulans*, or any other probiotic supplement will be excluded unless they have undergone the specified washout. The strict eligibility criteria is designed to reduce confounders on immune health affecting both upper respiratory tract infections and gastrointestinal tract infection symptoms. Children presenting with any other medical condition or lifestyle factor which may affect the safety of their participation or study outcomes will also be excluded.

5 STUDY OBJECTIVES

The objective of this study is to investigate the safety and efficacy of *Bacillus coagulans* SNZ 1969 on the incidence rate, duration, and severity of acute upper respiratory tract infections (URTI) and gastrointestinal tract infection (GITI) symptoms in healthy school-aged children.

Primary outcomes:

- 1. The difference in incidence, duration, and severity (area-under-the-curve (AUC)) of URTI as assessed by the Canadian Acute Respiratory Illness and Flu Scale (CARIFS) from baseline to day 84 between *Bacillus coagulans* SNZ 1969 and placebo
- 2. The difference in incidence, duration, and severity (area-under-the-curve (AUC)) of Additional Respiratory Tract Symptoms as assessed by Additional Respiratory Tract Symptoms questionnare from baseline to day 84 between *Bacillus coagulans* SNZ 1969 and placebo
- 3. The difference in incidence, duration, and severity (AUC) of GITI symptoms as assessed by the GITI Symptoms Questionnaire from baseline to day 84 between *Bacillus coagulans* SNZ 1969 and placebo

Secondary outcomes:

[figure not shown]
- 1. The difference in incidence, duration, and severity (AUC) of URTI as assessed by the CARIFS from baseline to days 28 and 56 between *B coagulans* SNZ 1969 and placebo
- 2. The difference in incidence, duration, and severity (AUC) of Additional Respiratory tract symptoms as assessed by Additional Respiratory Tract Symptoms questionnare from baseline to days 28 and 56 between *B coagulans* SNZ 1969 and placebo
- 3. The difference in incidence, duration, and severity (AUC) of GITI symptoms as assessed by the GITI Symptoms Questionnaire from baseline to days 28 and 56 between *B. coagulans* SNZ 1969 and placebo
- 4. The difference between *B. coagulans* SNZ 1969 and placebo from baseline to days 28, 56, and 84 on:
 - a. Severity of cold/flu and GITI symptoms as assessed by total and individual daily symptom scores
 - b. Number of missed school days
 - c. Number of well days, related to the absence of cold/flu and GITI symptoms
 - d. Use of prescription and non-prescription cold/flu medications to treat cold or flu symptoms
 - e. Total days of illness
- 5. The difference in change between B. coagulans SNZ 1969 and placebo from baseline to day 84 on:
 - a. Saliva secretory immunoglobulin A (sIgA) concentrations
 - b. Serum levels of Immunoglobulin A (IgA), G (IgG), E (IgE) and M (IgM)
 - c. Immune response biomarkers: CD14, CD163, CD40 (TNFRSF5), CRP (C-Reactive Protein), E-Selectin, Fas (TNFRSF6/Apo-1), Fas Ligand (TNFSF6), GCSF, ICAM-1 (CD54), IL-1 alpha (IL-1 F1), IL-1 beta (IL-1 F2), IL-1 R4 (ST2), IL-10, IL-12 p70, IL-13, IL18, IL-2, IL-2 R alpha, IL-4, IL-6, IL-8 (CXCL8), Lipocalin-2 (NGAL), MCP-1 (CCL2), MCP-2 (CCL8), MIF, MIP-1 alpha (CCL3), MIP-1 beta (CCL4), Osteopontin (SPP1), PAI-1, Platelet Factor 4 (CXCL4), Procalcitonin, RAGE, Resistin, Thrombomodulin, TNF alpha, TREM-1, Troponin I, uPAR, VCAM-1 (CD106), VEGF-A.
 - d. Microbiome as assessed by 16s rRNA fecal microbiome analysis

Safety outcomes:

- 1. Incidence of post-emergent adverse events (AE)
- 2. Clinically relevant changes in vital signs (blood pressure (BP) and heart rate (HR)) after supplementation

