7.4 Early Withdrawal

Personal reasons

As stated in the Informed Consent Form (ICF), a participant may withdraw from the study for any reason at any time.

Removal by Qualified Investigator

Participant discontinuation should be considered at the discretion of the Qualified Investigator. The circumstances of any discontinuation must be documented in detail in the participant file and final report. If possible, the evaluations planned for the end of study will be carried out at the time when the participant is withdrawn from the study.

Criteria for removal of participants from the study includes:

Clinical reasons

A participant may be withdrawn from the study if, in the opinion of the Qualified Investigator, it is not in the participant's best interest to continue. Any participant who experiences a serious adverse event (SAE) may be withdrawn from the study at the discretion of the Qualified Investigator. A participant will also be withdrawn due to AEs causing clinically significant illness or the need for prohibited medication(s) during the study. Any participant who becomes pregnant during the course of the study will be withdrawn and followed up with until giving birth.

Protocol violation

Any participant found to have entered this study in violation of the protocol will be discontinued from the study at the discretion of the Qualified Investigator. This will include any participant found to have been inappropriately enrolled (did not meet eligibility criteria). Participant non-compliance includes failure to show up for study visits, failure to take the investigational product as directed, or refusal to undergo study visit procedures. Participants who are found to be taking prohibited medications or supplements without the knowledge of the Qualified Investigator will also be withdrawn. Any major protocol deviations (i.e. those that increase the risk to participants and/or compromise the integrity of the study or its results) will result in participant discontinuation.

Participant Replacement

For all early withdrawals, a participant leaving the study prematurely or in the event of participant removal will NOT be replaced by unless attrition rates are high. It is understood by all concerned that an excessive rate of withdrawals can render the study un-interpretable, thus unnecessary withdrawal of participants should be avoided.

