9.7.6 Study Diary

Participant caregiver's will be instructed to complete the study diary daily. Questions pertaining to IP compliance, lifestyle habits, concomitant medications (inclusive of OTC medications and vaccinations), tracking cold/flu and GITI symptoms (see Sections 9.7.7, 9.7.8, and 9.7.9 below), missed school days, and any adverse events and symptoms throughout the study will be included. Each day, caregivers will ask if their child has any of the symptoms listed in the CARIFS, Additional Respiratory Tract Symptoms or GITI Symptom Questionnaires (Sections 16.1, 16.2, and 16.3). Caregivers will report all symptoms in the study diary daily using the CARIFS, Additional Respiratory Tract Symptoms, and GITI Symptoms Questionnaires.

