11 STATISTICAL EVALUATION

11.1 Determination of Sample Size

Assuming placebo participants would experience 1.43 episodes of URTIs and 7.42 duration days of URTI symptoms during 84 days of follow up (22), a sample size of 100 participants (50 participants per arm) has a power of 80% to detect a rate of \leq 0.76 for the number of episodes of URTIs and \leq 5.80 for the duration days of URTI symptoms in the Bacillus coagulans SNZ 1969 group using Poisson regression model.

In addition, a sample size of 100 participants could detect an effect size ≥ 0.63 in the AUC of GITI symptom scores and in the AUC of the Additional Respiratory Tract Symptoms questionnaire, and a difference of ≥27.8 score.day in the mean of AUC of CARIFS daily total symptom scores between Bacillus coagulans SNZ 1969 and placebo groups assuming standard deviations equal to 52.96 and 32.85 score.day for Bacillus coagulans SNZ 1969 and placebo groups (22), respectively, using two-sample t-test with 80% power, 2-sided 5% significance level, and 20% dropout rate.

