11.3 Statistical Analysis Plan

For both count and continuous primary and secondary outcomes, summary statistics including number of participants, mean, median, standard deviation, first quartile, third quartile, minimum, and maximum will be obtained for each available time interval and for each group. For categorical outcomes, frequencies and percentages will be presented.

The difference in the number of incidences of URTI, duration days of URTI, missed school days, well days, illness days between Bacillus coagulans SNZ 1969 and Placebo groups will be assessed by computing the rate ratio with 95% confidence interval using a generalized linear model with log link function (Poisson or negative binomial regression model).

The difference in the number of incidences of Additional Respiratory Symptoms and the duration days of Additional Respiratory Symptoms between Bacillus coagulans SNZ 1969 and Placebo groups will be assessed by computing the rate ratio with 95% confidence interval using a generalized linear model with log link function (Poisson or negative binomial regression model).

The difference in the number of incidences of GITI symptoms, duration days of GITI symptoms, missed school days, well days, illness days between Bacillus coagulans SNZ 1969 and Placebo groups will be assessed by computing the rate ratio with 95% confidence interval using a generalized linear model with log link function (Poisson or negative binomial regression model).

The difference in the AUC for daily total CARIFS scores, the mean total severity scores of URTI symptoms, the AUC for daily total Additional Respiratory Tract Symptoms questionnaire scores, the AUC of GITI symptom scores, and mean of GITI symptom scores between Bacillus coagulans SNZ 1969 and Placebo groups will be assessed by two-sample t-test if the outcome is normally distributed and Wilcoxon's rank sum test if the outcome is not normally distributed. Normality assumption will be assessed using quantile-quantile (Q-Q) plots.

Fisher's exact test will be used to assess the difference of proportion of participants who used prescription and non-prescription cold/flu medications to treat URTI/GITI symptoms between Bacillus coagulans SNZ 1969 and Placebo. 95% confidence interval of odds ratio will be calculated.

Differences between groups for sIgA, IgA, IgG, IgE, IgM, and immune response biomarkers at day 84 will be assessed by ANCOVA model adjusting for baseline values.

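### The immune-marker ANCOVA adjusts only for the baseline value and leaves unused the diary record of who was ill at each draw, which can cost power for markers that rise during a cold

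*Protocol*

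**What the plan says.** Section 5, secondary outcome 5, is "The difference in change between B. coagulans SNZ 1969 and placebo from baseline to day 84 on" salivary sIgA, the serum immunoglobulins, the immune response biomarkers and the microbiome. The biomarker list opens with "Immune response biomarkers: CD14, CD163, CD40 (TNFRSF5), CRP (C-Reactive Protein), E-Selectin" and also contains IL-6, IL-8, lipocalin-2 and procalcitonin.

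Sections 9.3, 9.6 and 9.9 place the blood and saliva samples at Day 0 and at Day 84 ± 2 (or at early termination). They do not say what happens if the child is ill that day. Section 9.3 includes a review of current health status; the Visit 5 list in section 9.6 does not. The introduction says the trial is run in the 2025-2026 cold and flu season so that children are exposed.

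Section 11.3 fixes the analysis: "biomarkers at day 84 will be assessed by ANCOVA model adjusting for baseline values". No other covariate is named. If the diagnostic plots are poor, ranks or another transformation of the dependent variable are used.

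Illness is already recorded. In section 9.7.6, "Caregivers will report all symptoms in the study diary daily", and sections 9.2 and 9.7.7 extend this through run-in and the whole study period.

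**The concern.** Several of these markers are expected to respond to acute infection. A child with a cold at Day 84 then contributes an outlying result. A child with a cold at Day 0 contributes a baseline that misrepresents the usual level, which weakens the adjustment meant to provide precision. Both add noise to a comparison of about 40 children per arm.

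Interpretation is also affected. The introduction links marker changes in an earlier trial to its clinical benefit, so the marker results here are likely to be read as mechanism. The product is meant to reduce illness, so part of any Day 84 difference could arise because fewer active children had a cold that day. The model as written cannot tell that apart from a direct effect on the marker.

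**Working it through.** **1. Reproducing the protocol's figures.** Section 11.1 states "a sample size of 100 participants (50 participants per arm) has a power of 80% to detect a rate of" 0.76 against 1.43 episodes. It gives duration as 5.80 against "7.42 duration days of URTI symptoms during 84 days of follow up" and sizes the AUC outcomes "using two-sample t-test with 80% power, 2-sided 5% significance level, and 20% dropout rate". With 50 × 0.8 = 40 per arm:
- Episodes: ln(1.43/0.76) = 0.632; SE = √(1/(40×1.43) + 1/(40×0.76)) = 0.224; power = Φ(0.632/0.224 − 1.96) = 80.4%.
- Days: ln(7.42/5.80) = 0.246; SE = √(1/(40×7.42) + 1/(40×5.80)) = 0.0876; power = 80.3%.
- Effect size 0.63: Φ(0.63 × √(40/2) − 1.96) = 80.4%.

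All reproduce. No power figure is given for any biomarker. The days figure reproduces when 7.42 and 5.80 are taken as total days per child, so that reading is used below.

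**2. Children in a URTI on a given day.** Placebo: 7.42/84 = 8.8%, or 3.5 of 40. Active: 5.80/84 = 6.9%, or 2.8 of 40. These count URTI only.

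**3. Effect on precision.** Assume illness adds k well-child SDs on the analysis scale and the Day 0 to Day 84 correlation is r. With p ill, the variance becomes V = 1 + p(1−p)k², where p(1−p) = 0.088 × 0.912 = 0.0805. After baseline adjustment the residual variance is V − r²/V. Take r = 0.5, p = 8.8% in both arms and an effect of 0.63 × √0.75 = 0.546, which has 80% power if every child is well:

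| k | V | Residual variance | SE = √(2 × residual/40) | Φ(0.546/SE − 1.96) |
|---|---|---|---|---|
| 0 | 1.00 | 0.750 | 0.194 | 80% |
| 1 | 1.08 | 0.849 | 0.206 | 75% |
| 2 | 1.32 | 1.133 | 0.238 | 63% |
| 3 | 1.72 | 1.580 | 0.281 | 49% |

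Simulation of the same setting (4,000 trials per cell) gave 74%, 60% and 48% at k = 1, 2 and 3, and 29% at k = 5. Other simulations, with 8.8% and 6.9% ill at Day 84, gave 73-77%, 54-65% and 41-51% for r from 0.5 to 0.7, and 71-75%, 56-64% and 42-51% in a separate run. Together these give 71-77%, 54-65% and 41-51%.

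**4. The rank fallback.** At 8.8% ill and r = 0.5, rank ANCOVA gave 71%, 61%, 56% and 54% at k = 1, 2, 3 and 5, against 74%, 60%, 48% and 29% for the untransformed model. It limits the loss only from about k = 3.

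**5. Shift from unequal illness alone.** (8.8% − 6.9%) × k = 0.0193k, which is 0.02, 0.04 and 0.06 SD at k = 1, 2 and 3. With no direct effect, simulated rejection was 5.3-5.5%. If 7.42 and 5.80 were instead days per episode, the shares would be 1.43 × 7.42/84 = 12.6% and 0.76 × 5.80/84 = 5.2%. The shift would then be 0.07, 0.15 and 0.22 SD, with rejection of 6.5-12%.

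**6. What a flag recovers.** SD of the treatment estimate under the model as written, with the Day 0 flag added, and with both flags added:
- r = 0.5, k = 2: 0.235, 0.231, 0.198 (0.194 with no illness).
- r = 0.7, k = 2: 0.219, 0.203, 0.163 (0.160 with no illness).

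Over k = 1 to 3, the Day 0 flag alone is worth 0-6 power points. Both flags together restore about 77-80%, provided they identify the ill children correctly.

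**7. Flag accuracy.** At r = 0.7 and k = 2, power with both flags was 79% with no false flags, 65% if 20% of well children were wrongly flagged and 62% if 40% were, against 62-63% in that run for the model as written. At k = 3 it was 80%, 52% and 49%, against 48-50%. The false-flag shares are assumptions.

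**The case against.** The strongest reply is that a baseline-adjusted ANCOVA of a randomised comparison is not wrong, and that extra covariates and sensitivity analyses usually sit in a statistical analysis plan, which is not shown here. That stands to this extent: the protocol makes no error, and the point is an inexpensive improvement to a model it does state.

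The size of the loss also depends on k, for which the protocol has no figure. At k = 1 the loss is only 3-9 points, and a marker that does not move during a cold loses nothing. The Day 0 illness share may be below 8.8%, because health status and eligibility are reviewed at that visit. Most of the recoverable power comes from the Day 84 flag, which is post-randomisation and may itself be changed by the product. That analysis therefore answers a different question and cannot replace the main one.

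Two stronger readings are tempting and are not supported:
- A reader might infer that a marker difference cannot be read as immune modulation at all. The randomised contrast is a valid total effect, and on the total-days reading illness mix moves it by only 0.02-0.06 SD, with rejection close to 5%.
- A reader might infer from section 7.4, where if possible "the evaluations planned for the end of study will be carried out at the time when the participant is withdrawn", that samples taken at withdrawal are analysed as Day 84 values. No section says so, and section 11.3 refers to day 84.

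**Conclusion.** The point holds as a limited one about secondary outcomes; the primary conclusions are untouched. The protocol expects illness on sampling days and records it, but the marker model does not use it. For markers that move by about 2 SD or more during a cold, the loss is roughly 15 to 39 points from 80% over k = 2 to 3. For markers that move by 1 SD or less it is small or nil. The main comparison remains valid as a total effect but cannot separate a direct effect on the marker from fewer ill children on the draw day.

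This rests on 40 evaluable children per arm, the total-days reading of 7.42 and 5.80, r between 0.5 and 0.7, and the assumed k. It counts URTI only; gastrointestinal illness and markers still raised after a cold would add to the illness share.

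**What to change.** In section 11.3:
- Derive from the diary an ill-at-sampling flag for each draw. A child is flagged if the draw day lies inside a CARIFS-defined URTI, or inside an acute gastrointestinal illness defined by a restricted item set such as vomiting or diarrhoea. Any GITI item above 0 is too broad: the questionnaire in section 16.1 includes flatulence, burping and bad breath, and false flags remove most of the benefit (step 7).
- Use only diary days up to and including the draw. This keeps the Day 0 flag strictly pre-randomisation. Say how symptoms that first appear on the draw day are handled, since the CARIFS definition needs two consecutive days.
- Add the Day 0 flag to the main ANCOVA beside the baseline value.
- Pre-specify one supplementary analysis that also includes the Day 84 flag. Label it as conditioning on a post-randomisation variable, and use it for interpretation only, not as a condition for accepting the main result.

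The cost is two derived variables and one extra analysis, with no new samples or visits. The definitions should be fixed before unblinding so that the handling of ill children cannot look selective.
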